
#### Spectroscopy methods:

MRSI will be performed using standard techniques on a 3T Achieva (Philips Healthcare Inc.) system equipped with a 32-channel head coil (InVivo). Metabolite concentrations will be measured from selected brain regions. The scanner will be operating within FDA allowed guidelines for RF power deposition, dB/dt, and acoustic noise at all times. The whole scanning session including acquisition of structural data as well as all spectroscopy sequences of interest will last about 1 hour. Scanning sessions will be performed at the beginning of enrollment, before and after each 5-day (or 15-day) tDCS treatment and at follow-up intervals for up to 8 sessions per participant over a period of 1.5 years. Spectroscopy data will be analyzed by members of the study-team from the Departments of Radiology and Biostatistics using standard procedures.

#### Plasma BDNF Methods:

Approximately ten ml of venous blood will be drawn into an EDTA tube and centrifuged to generate plasma. Pre-analytical factors for blood collection and storage for extracellular vesicles (EV) biomarkers analysis will be in accordance with published guidelines (see Witwer et al., 2013, 2017). Collection will take place in an outpatient lab at Johns Hopkins Bayview Medical Center by experienced staff.

Isolation and enrichment of plasma will follow the protocol published in Mustapic et al., 2017. Enzyme linked immunosorbent assays (ELISA) may be performed to quantify additional exploratory biomarkers. All analyses will be conducted by members in the Department of Genetic Medicine and Geriatric Medicine and Gerontology.

#### Saliva BDNF methods:

BDNF val66met rs6265 genotyping will be done by Taqman analysis of either the entire sample at the same time or at different timepoints. To genotype BDNF and APOE (genotype determined with 2 SNPs) by Taqman analysis we will purchase saliva tubes provided by DNA Genotek (oragen 500, DNA collection kits) and we will send them to participants homes with a paid return address at our lab. We will include those participants who had agreed to be contacted for future research.

#### Analyses

On careful consideration of the literature and consideration of the degenerative nature of the disease, its variability, and the poorly understood effects of tDCS we have selected a within-subject, cross-over design. This design is the one most commonly used in tDCS studies (below we discuss reasons for excluding a tDCS-only condition). Furthermore, in consultation with the 3 study team statisticians we evaluated whether this design would be appropriate given our preliminary data. As shown in preliminary study #1, the carry-over effect between the first period and the others is small and in this situation a cross-over design is recommended (Liang & Zeger, 1986). In the within-subject crossover protocol, each participant will be administered three experimental conditions: Control (natural progression), IFG tDCS+language (henceforth abbr. tDCS treatment) (word production) and sham tDCS+language (henceforth abbr. tDCS treatment) (word production) and sham tDCS+language (henceforth abbr. tDCS treatment). To achieve an accurate estimate of degeneration and rate of decline in each participant at their particular stage of the disease progression, each participant will first be enrolled in the control condition (natural progression). All analyses, behavioral and imaging, will be under the oversight of the study statisticians.

The genetic analysis will be done under the supervision of [name] and DNA samples will be provided by the Genetic Core facility at Johns Hopkins University. Based on previous research supporting that BDNF modulates tDCS outcome we will focus our analysis on the BDNF (/Val/Met polymorphism) and regulatory variants in closely functionally related genes. Final decisions will be made immediately before genotyping. To give an example, we may use the BDNF protein association network from the STRING functional protein association networks database (https://string-db.org/), a curated database providing valid expandable information on functional gene networks. Genetic variants that regulate these genes are

then identified from public gene expression databases such as GTEx (https://gtexportal.org), which report variants whose genotype correlates strongly with gene expression across tissue types, i.e. they are expression quantitative trait loci – eQTLS).

Saliva samples will also be analyzed by the Genetic Core facility at Johns Hopkins University. DNA is setup in a format suitable for genotyping, called 'plating'. They will be genotyping all samples in one or more batches. Genotyping is completed using the most appropriate method for the polymorphism of interest. For the BDNF and APOE4 polymorphisms they will use Taqman analysis. Genotyping can be carried out in small batches or at the end of the study collection. At the end is most economical, small batches is costly). DNA is returned to the customer or can be stored long term in our biorepository for an annual fee.

## b. Study duration and number of study visits required of research participants.

Before any intervention participants will be enrolled in a control condition for 12 weeks during which no therapy will be provided to enable us to assess their personal decline rate. After this period they will be randomly assigned to either sham or tDCS experimental conditions. Three pre-training sessions may be proposed to test the tDCS experimental conditions before training. After 1-3 weeks of tDCS application (3-5 sessions in a week, 5-15 sessions per stimulation site) there will be an interval of approximately 2 months and then we will implement the other two tDCS conditions in a within-subject cross-over design, an example of which is shown in Table1. We will follow-up the participants with 2-week, 2-month and a final 6-month follow-up sessions. For those participants who are long-distance, at the 2-week time point we may use a video conferencing tool such as GoToMeeting to administer the assessments. This is to mitigate the costs of travel for a short appointment. In these sessions we will administer the behavioral therapy assessment as described in the therapy section. We will test participants with both the practiced items and unpracticed items to look at generalization effects to untrained items. Given that we will test each participant in different conditions, an example of the sequence of conditions is shown in Table 1. After the final evaluation of interventions, we will offer an optional remote extension phase. This will consist of 18 additional months of intervention: 50 therapy sessions+tDCS (in 10 weeks) every 3 approximately months for a 18-month period, depending on availability, using different areas of stimulation (either the IFG, SMG, MTG, or DLPFC or Precuneus based on previous literature, see above in tDCS methods for details) for up to 18 months in total. We will complete another full evaluation of language and cognitive skills at the end of the stimulation phase. We will compare maintenance of therapy gains for individuals who participate in these remote sessions to those who do not, to answer the question whether tDCS effects may be extended beyond the initial 2-month period follow-up, up to 18 months and whether the rate of decline may change. This is very important because long periods of interventions and followup are needed in studying intervention outcomes in a neurodegenerative disorder.

Table 1: Timecourse of interventions (18 sessions) and evaluations for two groups of participants in the crossover design (W: Week, LIFG: left inferior frontal gyrus, LMTG: left middle temporal gyrus, LIPL: left inferior parietal gyrus; eval (b+a): evaluation before and after or evaluation only; 18: number of sessions).

Time	W1-12	W14-20	W22-24	W27	W233-35	W38	W44	W61
Group 1: control then sham then tDCS	Control	1 sham 1 LMTG 1 LIPL	15 sham	2 w eval	15 LIFG	2 w eval	2 m eval	6 m eval
Group 2: control then tDCS then sham	Control	1 sham 1 LMTG 1 LIPL	15 LIFG	2 w eval	15 sham	2 w eval	2 m eval	6 m eval

Both Groups eva	val (b+a) eval (b+a) eval (b+a)	Eval eval (b+a)	eval Eval	val
-----------------	---------------------------------	-----------------	-----------	-----

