#### f. Definition of treatment failure or participant removal criteria

Participants will be removed from the study if they are unable to comply with task instructions or tolerate the tDCS procedure.

g. Description of what happens to participants receiving therapy when study ends or if a participant's participation in the study ends prematurely

When the study ends participants will continue to receive management with [name] as usual (follow-ups every 6 months with language and behavioral assessments). If a patient's participation in the study ends prematurely s/he will still receive care as before. In sum, termination of the study or termination of participation in it will not affect regular therapy he or she may be receiving.

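### The optional remote extension compares joiners with decliners and is said to answer a question about tDCS, but that contrast mixes tDCS with extra therapy and with self-selection

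*Combined protocol and SAP*

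**What the plan says.** All the relevant text on the extension is in Section 3b (study duration and number of visits).

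- Entry is voluntary: "After the final evaluation of interventions, we will offer an optional remote extension phase".
- Content is a package: "50 therapy sessions+tDCS (in 10 weeks) every 3 approximately months for a 18-month period, depending on availability". The listed stimulation sites are all active; no sham or therapy-alone arm is described for this phase.
- The comparison: "We will compare maintenance of therapy gains for individuals who participate in these remote sessions to those who do not".
- Its purpose: "to answer the question whether tDCS effects may be extended beyond the initial 2-month period follow-up, up to 18 months". The same sentence adds whether the rate of decline may change.
- Outcome timing: "We will complete another full evaluation of language and cognitive skills at the end of the stimulation phase". No matching research evaluation is stated for people who decline.

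Three other places bear on it. Section 3g says that when the study ends participants return to usual management, with "follow-ups every 6 months with language and behavioral assessments". Section 6c, the statistical plan, deals only with the crossover, at immediate, 2-week and 2-month follow-up. Its one regression asks whether tDCS effects differ by characteristics such as age and atrophy. Hypothesis 1a (Objectives) expects behavioural therapy without tDCS to improve language too.

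**The concern.** The randomised part of the trial uses sham so that therapy and stimulation can be told apart. The extension drops that control but keeps the wording of a tDCS question. Two separate problems follow.

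**Bundling.** The contrast is therapy plus tDCS against no study sessions. The plan itself treats therapy as active, so even perfectly comparable groups would not reveal which component produced a difference.

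**Self-selection.** Whether someone takes up repeated 10-week blocks, and how many, depends on choice and availability. Severity, speed of decline and support at home could all influence that. Remote sessions involve trained participants and spouses and live video (Section 3a, tDCS methods), so spousal support is a concrete route. In a progressive disease the same factors can also predict the outcome.

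At stake is the plan's 18-month conclusion. Section 3b describes long intervention and follow-up as very important, and this comparison is the only route it gives to a claim at that horizon.

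**Working it through.** **The plan's own figure.** No sample size, alpha or power is given for the extension. The nearest figure is the crossover's 75% power in Section 6c (30 participants, design effect 1.5, effect size 0.8). It reproduces: 30 × 1.5 = 45 effective participants, 22.5 per arm, and a two-sided 5% t-test (alpha and sidedness assumed) gives 74.6%. That calculation concerns tDCS against sham within people and gives no support to a comparison of joiners with decliners.

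**Bundling: the difference in therapy exposure.** Section 3b can be read in two ways.

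- A block starts every 3 months: 18 / 3 = 6 blocks, and 6 × 50 = 300 sessions.
- A 3-month gap (13 weeks) follows each 10-week block: 78 / (10 + 13) = 3.4, so 3 to 4 blocks, or 150 to 200 sessions.

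Joiners could therefore receive roughly 150 to 300 study therapy sessions, each with tDCS, and decliners none. In the Table 1 example the main crossover conditions have 15 sham and 15 active sessions. Therapy and tDCS rise together in every joiner, so no analysis of this contrast can separate them.

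**Selection: an illustration.** The assumptions, none of them from the documents, are:

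- opting in correlates r with the later course (normal latent variable);
- half of people join;
- the crossover's 30 participants split 15 and 15, all assessed;
- an unadjusted two-sided 5% t-test is used;
- the overall SD stands in for the within-group SD;
- neither therapy nor tDCS has any effect.

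Group difference: d = 2 × 0.798 × r = 1.596r SD.
Noncentrality: d × √(15 × 15 / 30) = 2.739d, with 28 degrees of freedom and critical value 2.048.

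| r | d (SD) | Noncentrality | Chance of significance |
|---|---|---|---|
| 0.1 | 0.16 | 0.44 | 7% |
| 0.2 | 0.32 | 0.87 | 13.5% |
| 0.3 | 0.48 | 1.31 | 24.5% |
| 0.4 | 0.64 | 1.75 | 39% |

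Holding d at the last three values, a 20/10 split gives 12.5%, 22.3% and 35.7%. If r has the opposite sign the percentages are the same but the spurious result favours decliners, and a real benefit could be hidden. The table covers selection only; any benefit of the extra therapy comes on top.

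**Does anything elsewhere repair this?** Randomisation in Section 3b assigns the crossover conditions, not entry to the extension. The regression in Section 6c is for effect modification, not for differences between those who join and those who do not. The one useful resource is the 12-week control phase, designed to measure "their personal decline rate", but the plan does not link it to this comparison.

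**The case against.** The best defence is that this is a peripheral analysis. It is absent from the primary outcomes, secondary outcomes and statistical plan, it sits in a section on visits, and its question is worded cautiously. That stands, and it limits the importance of the point. It does not remove the mismatch between the comparison and the question it is said to answer. The part about rate of decline is not worded as specific to tDCS, but it carries the same selection problem.

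A reader might also infer more than the text supports:

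- *That the comparison will be unadjusted.* No method is named. Adjustment is unspecified, not ruled out, and Section 3a puts all analyses under the study statisticians.
- *That decliners get no therapy.* They get no study sessions. Sections 3d and 3g leave any outside therapy undisturbed.
- *That the plan rules out sham.* It describes none for the extension, although Section 3a describes coded sham blinding on the remote devices.
- *That the bias must flatter tDCS.* People who are worsening might be the ones who seek more treatment. The documents do not settle the direction.
- *That 7% to 39% is this trial's error rate.* The arithmetic is sound, but every input to it is assumed.

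**Conclusion.** The concern holds for the extension's stated conclusion. As described, a difference between joiners and decliners cannot be attributed to tDCS. The bundling argument rests on the text alone and needs no assumption. The selection argument rests on voluntary entry with no adjustment specified; its direction and size are unknown, and the 7% to 39% only shows that modest selection would matter in a group of this size.

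It might be tempting to read this as a flaw in the trial's evidence on tDCS as a whole. The documents do not support that: the randomised, sham-controlled crossover and the Section 6a primary outcomes do not depend on the extension. The point should be fixed because the plan commits in advance to an interpretation that the contrast cannot give, and correcting it is cheap.

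**What to change.** - In Section 3b, label the joiner-versus-decliner comparison exploratory. Say that it estimates an observational association with the therapy-plus-tDCS package, and that tDCS-specific conclusions come from the sham-controlled crossover.
- In Section 6c, name the analysis and a small covariate set already collected: the end-of-crossover score and the decline rate from the 12-week control phase. With about 30 people a longer list would be fragile.
- State which assessments of non-joiners will be used. The usual 6-monthly follow-up in Section 3g offers language assessments; take the one closest in time to the joiners' final evaluation and compare only measures common to both.

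The cost is mainly wording, with no new study visits. The downsides are real:

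- The claim for the extension becomes weaker.
- A slope from evaluations before and after 12 weeks is a noisy covariate.
- Confounding will remain after adjustment, and no adjustment separates therapy from tDCS.
- Non-joiner assessments will match imperfectly in timing and possibly in content, since the documents do not say that the clinic visits include the trained-item probes.

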#### c. Blinding, including justification for blinding or not blinding the trial, if applicable.

Participants will be blinded to the application of anodal or sham tDCS. To achieve blinding, all participants will be fitted with the tDCS electrodes placed over the appropriate stimulation sites. As individuals typically experience a mild tingling sensation following the initiation of stimulation, both active and sham conditions will involve a ramping up of the current to appropriate intensity (1-2 mA) over 10-15 seconds to allow participants to habituate to the tingling sensation. At this point, the current will be ramped back down to 0 mA for individuals in the sham condition. Termination of the stimulation after the ramping up process is generally undetectable, and the brief duration of stimulation yields no functional effects. Staff who will be applying tDCS will also be blinded to the sham vs tDCS treatment condition.

d. Justification of why participants will not receive routine care or will have current therapy stopped

Participation in this study will not disrupt any current care or therapy.

#### e. Justification for inclusion of a placebo or non-treatment group

All participants will be participants with PPA from [name] database or participants with MCI from [name] clinic who will undergo active and sham conditions, thus serving as their own control.

#### f. Definition of treatment failure or participant removal criteria

Participants will be removed from the study if they are unable to comply with task instructions or tolerate the tDCS procedure.

g. Description of what happens to participants receiving therapy when study ends or if a participant's participation in the study ends prematurely

When the study ends participants will continue to receive management with [name] as usual (follow-ups every 6 months with language and behavioral assessments). If a patient's participation in the study ends prematurely s/he will still receive care as before. In sum, termination of the study or termination of participation in it will not affect regular therapy he or she may be receiving.

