conditioning using tDCS have received Johns Hopkins IRB approval. We will use either the same equipment as [name] and his team have used (a Chattanooga lonto Device) as well as the same application technique, recently acquired state-of-the-art device using special software for doubleblinding (Soterix 1x1 CT: clinical trials), or a Neuroelectrics Starstim 8 device, which is a high-definition tDCS cap with higher precision. In order to administer intervention during the global pandemic and in a virtual manner, we will offer the option of remote stimulation (Soterix mini-CT device and MIND STIM+, YBrain). Attached please find letters from Clinical Engineering documenting that the tDCS devices have undergone clinical inspection as well as the manuals. When remote devices are implemented, participants and spouses will be trained prior to intervention and sessions will be conducted in real-time via video conference (e.g., Zoom). Stimulation will be delivered at an intensity of 1-2mA (estimated current density 0.04 mA/cm2; estimated total charge 0.048C/cm2) for a maximum of 20 minutes in the tDCS groups and for a maximum of 30 seconds in the Sham group. For both interventions (tDCS and Sham) the electrical current will be increased in a ramp-like fashion at the onset of the stimulation eliciting a transient tingling sensation on the scalp that usually disappears over seconds. Although the ramping process requires the researcher's input, it is now feasible to blind study staff who will be applying tDCS, as well as participants, as we now have a box that allows another member of the team to set the box to "tDCS" or "sham" without the knowledge of the researcher providing the therapy. In the Starstim 8 and remote devices, double-blinding is achieved through codes known only to the PI who is not administering any stimulation or evaluation, so both the technician or professional who administers the stimulation and evaluation are blind to the current condition being either actual tDCS or sham. After the ramping, in the sham condition, the intensity drops to 0 mA. These procedures have been shown to successfully blind participants as to whether they were members of experimental or control groups (Gandiga et al., 2006). The sites of tDCS application will be determined by the type of therapy used and the PPA variant group or MCI and will be either the inferior frontal gyrus (IFG), the supramarginal gyrus (SMG), or the middle temporal gyrus (MTG) or a combination as shown in the literature. A recent meta-analysis of the functional neuroimaging literature on spelling has not yet identified clearly the neural substrates for PG conversion; the most plausible network includes the inferior parietal lobule including the supramarginal gyrus (Purcell et al., 2011). This area has also been identified as a critical area for spelling in the lesion literature as well. Another plausible area that shows activations during both PG conversion and lexical (word) spelling is the inferior frontal gyrus (IFG) (Purcell et al., 2011) and lesions in the IFG are associated with impaired PG conversion (Beeson et al., 2010). The stimulation site of IFG will be determined between F7 and F8 electrodes and that of SMG between TP3 and TP4 using the EEG 10-20 electrode position system (Homan, 1988). Additionally, studies have reported positive results of tDCS over the left dorsolateral prefrontal cortex (DLPFC) leading to improvement in attention deficits due to stroke, Parkinson's disease, and major depression (Boggio et al., 2006, 2007; Fregni et al., 2006; Kang et al., 2009). In addition to improving attention, anodal tDCS at the left DLPFC has been shown to improve working memory in TBI patients (Ulam et al., 2015). We hypothesize that anodal tDCS over the L DLPFC when administered in combination with cognitive training will improve language performance of PPA and MCI participants more than behavioral therapy alone, and that improvements may generalize to some other cognitive functions. The dependent variable will be the same baseline and post-therapy evaluation as described above that will take place before, after, 2 weeks and 2 months post-stimulation for each stimulation condition (see Table 1). These same areas, predominantly on the left, are activated during naming (Jarso et al., 2013) and working memory (Philipose et al., 2007). In most cases of PPA and all cases of MCI, we will stimulate areas of the left hemisphere that are not atrophied. In the most advanced cases of PPA, with severe left hemisphere atrophy, we will stimulate the same sites in the right hemisphere in order to stimulate its compensatory mechanisms (see Hypothesis 1d). By this design we will be able to achieve a within-subject design for all conditions as well as to evaluate immediate, short- and long-term effects of each stimulation site without confounds and without any carry-over effects. We will also conduct a 6-month language evaluation to assess the overall therapy gains.

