#### 4. Inclusion/Exclusion Criteria

Inclusion Criteria: Participants must be clinically diagnosed with svPPA, nfvPPA or lvPPA, unclassifiable PPA, or MCI. Diagnosis will be based on neuropsychological testing, language testing (most commonly the Western Aphasia Battery), MRI and clinical assessment. They must also be right-handed, speakers of English and have up to high-school education. Participants will be recruited from the [name] PPA database, one of the largest in the country or from [name] clinic or may be referred by other clinicians with a confirmed diagnosis of PPA or MCI. The age range of the participants will be 50-90 years old due to variability inherent in this neurodegenerative syndrome.

Exclusion Criteria: Potential participants will be excluded if they have uncorrected visual or hearing impairment by self report or stroke/other premorbid neurological or psychiatric disorder affecting the brain, or any other language-based learning disorder other than PPA. Potential participants will also be excluded from the spelling treatment if they were not premorbidly proficient spellers. Furthermore, participants in advanced stages of the disease will be excluded since it has been shown that at these stages most

language functions are very impaired (Sepelyak et al., 2011) and it will be difficult to see any results specific to the current therapeutic intervention. Furthermore, participants with pre-existing psychiatric disorders such as behavioral disturbances, severe depression, schizophrenia that do not allow them to comply or follow the study schedule and requirements such as repeated evaluation and therapy will be excluded. In addition, individuals with severe claustrophobia and cardiac pacemakers or ferromagnetic implants will be excluded from the MRI portion of the study since they may not tolerate the MRS sessions. Pregnant women will also be excluded. However, they could still participate in the treatment study without having the MRI scans.

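### Section 3f takes people out of the study, not only off the procedure, so a participant who stops in the second block but could still be tested loses the tDCS–sham pair needlessly

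*Combined protocol and SAP*

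**What the plan says.** Section 3f gives one rule with two triggers: "Participants will be removed from the study if they are unable to comply with task instructions or tolerate the tDCS procedure". Section 3g covers what follows an early end to participation and speaks only of care: if "participation in the study ends prematurely s/he will still receive care as before". It also mentions six-monthly clinic follow-up, but as usual management after the study. That follow-up is not tied to block times and is not described as measuring the trained and untrained items of section 6a.

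The outcome schedule under tDCS methods in section 3 calls for evaluations "before, after, 2 weeks and 2 months post-stimulation for each stimulation condition". Section 3b places randomisation after the 12-week control period: "After this period they will be randomly assigned to either sham or tDCS experimental conditions". Between blocks, "there will be an interval of approximately 2 months and then we will implement the other two tDCS conditions". Table 1 ("Timecourse of interventions (18 sessions) and evaluations for two groups of participants in the crossover design") runs to W61.

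Section 6c defines a change score for each condition, from just before treatment to each follow-up time. It tests whether the within-patient difference between active and sham change is centred at zero, permuting labels within each patient. The power statement is 75% for 30 participants, design effect 1.5 and effect size 0.8. It includes no allowance for loss, and section 6 gives no rule for incomplete pairs.

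**The concern.** The rule treats two decisions as one: stopping a procedure, and ceasing to be measured. A person who cannot tolerate stimulation, or cannot keep up with the therapy tasks, may still manage a short outcome assessment. Under 3f as worded they leave the study, and nothing in the schedule brings them back for the after-treatment evaluation.

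In a parallel-group trial that would cost one outcome. Here the unit of analysis is a pair, so a missing after-treatment score in block 2 also makes the block-1 result unusable in the paired test. With 30 participants and power of 75% before any loss, each pair counts. The contrast also comes to describe only people who stayed able to do the tasks through both blocks. An evaluation that was not done cannot be recovered later by analysis.

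**Working it through.** **Who loses a pair, and whether 3f is the cause.** In the two-condition design:

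- *Stops in block 1 or in the interval.* There is no second condition. The pair is lost whatever 3f says.
- *Stops during block 2.* The block-1 change and the block-2 starting value exist. Only the block-2 after-treatment evaluation is missing, and it is missing because none is planned after removal. This loss is due to 3f.
- *Removed after both after-treatment evaluations.* Only later time points are lost.

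In the three-condition option of section 6c, sham is never last. Removal in the third block therefore still leaves one active–sham contrast.

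**The plan's power.** Inputs from section 6c: N = 30, design effect 1.5, effect size 0.8. Assumed, because not stated: two-sided 5%. Participants per arm in the equivalent independent design = 1.5 × N / 2 = 22.5. A two-sample t-test gives 74.6% (normal approximation 76.5%), which reproduces the stated 75%.

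**Effect of lost pairs.** Same formula; the loss rates are assumptions:

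| Pairs lost | Pairs left | Per arm | Power |
|---|---|---|---|
| 0% | 30 | 22.5 | 74.6% |
| 10% | 27 | 20.25 | 69.9% |
| 20% | 24 | 18 | 64.5% |
| 30% | 21 | 15.75 | 58.4% |

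A paired t-test calibrated to 75% at 30 pairs gives 70.2%, 64.6% and 58.3% for the last three rows, so the choice of formula does not matter.

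**What the 3f wording recovers.** Assume that half of the stops fall in block 2.

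- *10% loss.* 3 pairs lost, 1.5 of them in block 2. All testable: 28.5 pairs, 72.4%, a gain of 2.5 points. Half testable: 27.75 pairs, 71.1%, a gain of 1.2 points.
- *20% loss.* 6 pairs lost, 3 of them in block 2. All testable: 27 pairs, 69.9%, a gain of 5.4 points. Half testable: 25.5 pairs, 67.3%, a gain of 2.8 points.

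These gains assume that restored pairs carry the full effect. Suppose instead that half of the block-2 stoppers were in an active block and kept none of it. At 20% loss with all testable, the average effect is (25.5 × 0.8 + 1.5 × 0) / 27 = 0.756, and power with 27 pairs is 65.0%, against 64.5% without the change. If they keep half, the average is (25.5 × 0.8 + 1.5 × 0.4) / 27 = 0.778, and power is 67.5%.

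**Bias in complete pairs.** A simulation of 500,000 people used normal change scores (mean 0.8 active, 0 sham, SD 1, correlation between blocks 0.3 to 0.7). The tendency to be removed was correlated 0.3 or 0.5 with change.

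- Removal following the person's average change over both blocks: the estimate stays at 0.80.
- Removal following the change in either block: 0.78–0.80, 0.76–0.79 and 0.75–0.79 at 10%, 20% and 30% loss.
- No true effect: 0.00.

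**The case against.** The strongest reply is that few people are recoverable. Someone who cannot follow task instructions mostly cannot give the primary outcome either, since that is task accuracy. Intolerance looks rare: the safety data in section 7a report only mild itching that never stopped a study. Several features also make removal less likely: the 12-week control period with evaluations before randomisation; the pre-training sessions, which Table 1 shows as identical in both groups; the phone screening in section 7b; and the exclusions in section 4, under which "participants in advanced stages of the disease will be excluded" along with people whose psychiatric disorder prevents compliance. All of this stands and keeps the point small. It does not remove it. None of these steps plans for someone who worsens after randomisation, and the protocol foresees removals, since it has a rule for them.

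It can also be said that 3g answers a question about care, not data collection, and that section 6c names a robust repeated-measures multivariate ANCOVA, which might use incomplete records. Both are fair. But no other section plans evaluations after removal, and the test that 6c specifies is built on the paired difference.

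A reader might infer more than the documents support:

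- *That 3f discards data already collected.* It does not say so.
- *That 3f causes every lost pair.* First-block stoppers have no second condition in any case.
- *That the rule biases the result towards tDCS.* This would need outcome-related removal specific to the active block, and the documents give no mechanism for it. An example in which a removed 20% have no effect (0.8 × 0.80 = 0.64 over everyone, against 0.80 in completers) assumes its conclusion and compares effects in two different populations.
- *That an all-randomised analysis is required.* A treatment-policy effect is a debatable choice here, and it is unclear how a block that was never started would be scored.

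**Conclusion.** The point holds as a minor, avoidable loss of precision. It concerns people who stop in block 2 and can still be tested. At an assumed 10–20% loss of pairs, with half the stops in block 2 and between half and all of those people testable, the wording change is worth about 1 to 5 points of power, and close to nothing if active-block stoppers keep no effect. Bias is probably negligible. The loss rate, the split between blocks, testability and the share of effect kept are all assumptions, because the documents give none of them. The 74.6% starting point rests on the plan's own inputs and an assumed two-sided 5% level. The change is worth making because it is cheap, not because the result is at risk.

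**What to change.** Reword 3f so that participants who meet the criterion stop the procedure concerned but, unless they withdraw, complete the remaining planned evaluations they can do for any block they have started. In Table 1 the 2-month evaluation after block 1 is not a separate visit; it roughly coincides with the evaluation before block 2. Allow video where it is usable: section 3b already provides, for long-distance participants, that "at the 2-week time point we may use a video conferencing tool such as GoToMeeting to administer the assessments". Record the block, the reason and whether the person could be tested, and report removals by condition. Who stops stimulation, and when, does not change.

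The costs are protocol wording and a few extra visits, some needing travel, since section 7e expects presence in Baltimore for follow-up. Some people will be untestable, above all those who cannot follow instructions. The estimate may be somewhat smaller, because partly treated blocks are included.

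A mixed model with treatment, period and participant effects on all randomised participants, alongside the permutation test, would also use block-1 stoppers. It is optional and not part of this fix. If it is added, state what effect it estimates and how unstarted blocks are handled.
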